4.1 Investigational Product

An investigational product, also known as investigational medicinal product in some regions, is defined a pharmaceutical form of an active substance or placebo being tested or used as a reference in a clinical study, including products already with a marketing authorization but used or assembled (formulated or packaged) differently than the authorized form, or used for an unauthorized indication, or when used to gain further information about the authorized form.

The investigational product should be stored in a secure area according to local regulations. It is the responsibility of the investigator to ensure that investigational product is only dispensed to study subjects. The investigational product must be dispensed only from official study sites by authorized personnel according to local regulations. Although not a medicinal product, Radiation Therapy is also considered part of study treatment.

In this protocol, investigational products are:

- BMS-936558 (nivolumab)
- Temozolomide

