Targeted Physical Examination, Vital Signs	Q2 wks	Day 1 of each cycle	Q2 wks x 8 doses, then Q4 wks	Weight, BP, HR, RR, temperature, and Karnofsky Performance Status
Adverse Events Assessment	Continuously			Record at each visit
Review of Concomitant Medications	X	X	X	Record at each visit, including steroid dose
Radiation Therapy	See Note		See Note	Total dose 60 Gy over 6-7 weeks, see Section 3.1.2.2
CBC with Differential	Weekly	Day1&22 of each cycle	Within 3 days prior to each dose	Weekly if delayed and as clinically indicated
Chemistry panel	Q4 wks	Day 1 each cycle	Within 3 days prior to each dose	Chemistry panel: AST, ALT, ALP, T.Bili, albumin, BUN or serum urea, creatinine, Ca, Na, K, Cl, LDH, Glucose Additional tests, as clinically indicated, will also be submitted
Thyroid Function Test		X	X	TSH every 8 weeks, T3 and T4 (Free or Total, if TSH abnormal) and as clinically indicated
Pregnancy Test [WOCBP only]	Every 4 weeks			Serum or urine pregnancy test every 4 weeks (± 3 days; minimum sensitivity 25 IU/L or equivalent units of HCG).
				
Tumor Assessment	X (See Note)			Contrast-enhanced MRI 4 weeks (± 7 days) after completing RT, then every 8 weeks (± 7 days) ^a until progression. See Section 5.4.1
				

Table 5.1-2: On-Treatment Assessments (CA209498)

Procedure	RT + TMZ	TMZ Maintenance	RT + Nivolumab	Notes: Windows refer to calendar days. Procedures must be done within 72h prior to dosing unless otherwise specified.
[REDACTED]		[REDACTED]		[REDACTED]
[REDACTED]		[REDACTED]		[REDACTED]
[REDACTED]		[REDACTED]		[REDACTED]
Health Care Resource Utilization		X (See Note)		Obtained prior to dosing Day 1 Week 1 and then with each MRI, (± 7 days) see Section 5.8.4
[REDACTED]		[REDACTED]		[REDACTED]
Dispense Nivolumab			X (see note)	Day 1 within 7 days of randomization, then every 2 weeks for 8 doses, then every 4 weeks
Dispense Temozolomide	D1, D15, D29 & D43 (if needed)	D1 each cycle		Temozolomide taken daily during RT then 4 week break, then daily x 5 in 28-day cycles x 6 cycles, see Section 4.5.2
Tumor Sample at time of progression or suspected progression	At time of PD or suspected PD			If biopsy or surgical resection is performed at progression or suspected progression, a tumor sample (block or slides) should be submitted for central neuropathologic review
Assess Temozolomide Compliance	X	X		Review medication diary

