6 STUDY PERIODS, TREATMENT REGIMENS AND POPULATIONS FOR ANALYSES

6.1 Study Periods

- Baseline period:
 - Baseline evaluations or events will be defined as evaluations or events that occur before the date and time of the first dose of study treatment. Evaluations (laboratory tests, pulse oximetry and vital signs) on the same date and time of the first dose of study treatment will be considered as baseline evaluations.
 - In cases where the time (onset time of event or evaluation time and dosing time) is missing or not collected, the following definitions will apply:
 - ◆ Pre-treatment AEs will be defined as AEs with an onset date prior to but not including the day of the first dose of study treatment
 - ◆ Baseline evaluations (laboratory tests, pulse oximetry and vital signs) will be defined as evaluations with a date on or prior to the day of first dose of study treatment
 - If there are multiple valid assessments on or prior to the first dose of study treatment:
 - ◆ For laboratory tests, the latest non missing labs value on or before first dose date (and time if collected) will be used as the baseline in the analyses. For 'LIPASE' and 'GLUCOSE', for treated subjects only, the last predose assessment with non-missing toxicity grade will be considered as baseline. If multiple assessments exist with the same collection date (and time if collected) and entry date and time, then the first observation is used as baseline.

- 
- 
- 
- Post baseline period:
 - On-treatment AEs will be defined as AEs with an onset date and time on or after the date and time of the first dose of study treatment (or with an onset date on or after the day of first dose of study treatment if time is not collected or is missing). For subjects who are off study treatment, AEs will be included if event occurred within a safety window of 30 days (or 100 days depending on the analysis) after the last dose of study treatment. No “subtracting rule” will be applied when an AE occurs both pre-treatment and post-treatment with the same preferred term and grade.
 - On-treatment evaluations (laboratory tests, pulse oximetry and vital signs) will be defined as evaluations taken after the day (and time, if collected and not missing) of first dose of study treatment. For subjects who are off study treatment, evaluations should be within a safety window of 30 days (or 100 days depending on the analysis) after the last dose of study treatment.

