For nivolumab and temozolomide: a by-subject listing of dosing of study medication (record of study medication, infusion details, and dose changes) and a listing of batch numbers will be also provided.

Radiotherapy

Duration of radiotherapy (in weeks): (Dose end date - Dose start date + 1) / 7

Cumulative dose (in Gy): sum of all the doses (Gy) administered to a subject as per CRF.

The following parameters will be summarized:

- Duration of radiotherapy (in weeks)
- Cumulative dose (in Gy)
- Number of subject that received less than 90% of planned dose

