APPENDIX 2 MISSING AND PARTIAL RADIOTHERAPY AND SURGERY DATES IMPUTATION ALGORITHMS

Procedures – Imputation Rules.

If reported procedure start date is a full valid date then set start date equal to the date part of procedure start date.

In case of partial date use imputation rules described below:

- If only day is missing then
 - If month and year of procedure match month and year of first dose date then impute as date of first dose;
 - If month and year of procedure don't match month and year of first dose date then impute as first day of that month and year.
- If both day and month are missing, then impute as maximum between 01JAN of the year and date of the first dose;
- If date is completely missing or invalid then leave missing.

Note: Imputation is not applicable to data where start date is not collected (for example "PRIOR RADIOTHERAPY" CRF). Set start date to missing in this case.

If reported end date is a full valid date then set end date equal to the date part of the reported end date.

In case of partial date use imputation rules described below:

- If reported end date is partial then set end date equal to the last possible reported end date based on the partial entered reported end date.
- If reported end date is missing, continuing, unknown or invalid then set end date equal to the most recent database extraction date.

If end date was imputed then compare end date to the death date or last known alive date if subject is not dead. If posterior then end date should be imputed to death date (or last known alive date if subject not dead).

Note: Imputation of partial dates only applies to data entered on "RADIOTHERAPY" CRF page. For other CRF pages in case of partial dates set end date to missing.

Surgeries – Imputation Rules.

If reported surgery date is a full valid date then set start date equal to the date part of surgery date.

In case of partial date, use one of the two imputation rules described below:

- 1) For data collected on "PRIOR SURGERY RELATED TO CANCER" CRF page:
 - a) If only day is missing then impute as the first day of the month;
 - b) If both day and month are missing then then impute as 01JAN of the year;

- c) If date is completely missing or invalid then leave missing.
- 2) B. For data collected on other CRF pages (deemed to be on-treatment/subsequent surgeries):
- a) If only day is missing then

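### SAP Appendix 2 runs a missing radiotherapy end date out to data extraction, death or last contact; if that rule feeds the SAP 7.4.1 exposure summary, a 6-7 week course is reported as a survival time

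*SAP*

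**What the plan says.** The procedures part of SAP Appendix 2 deals with end dates that are not full valid dates. For the worst case it states: "If reported end date is missing, continuing, unknown or invalid then set end date equal to the most recent database extraction date". An imputed end date is then compared with the date of death, or with the last known alive date for a subject not known to have died, and is moved back to that date if it falls later. A note limits the scope: "Imputation of partial dates only applies to data entered on 'RADIOTHERAPY' CRF page"; on other pages the end date is set to missing.

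The same appendix is more cautious elsewhere. A completely missing or invalid procedure start date stays missing, and so does a completely missing or invalid surgery date.

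The only visible analysis that uses a radiotherapy end date is in SAP 7.4.1: "Duration of radiotherapy (in weeks): (Dose end date - Dose start date + 1) / 7". Under SAP 7.1, continuous variables are summarized by mean, SD, median, minimum and maximum. The planned course in Protocol Table 5.1-2 is "Total dose 60 Gy over 6-7 weeks".

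**The concern.** The rule treats four situations alike. *Continuing* means that treatment had not stopped when the record was made, so an open end is defensible. *Missing*, *unknown* and *invalid* mean only that the date was not captured. Radiotherapy in this trial is a fixed course that finishes within about two months, and nothing visible bounds the imputed date by the planned length, the Gy recorded or the four-week break that follows in the temozolomide arm.

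If the rule supplies the end date for SAP 7.4.1, the reported duration for an affected subject no longer describes radiotherapy. It is the time from the start of radiotherapy to death or last contact. Both arms rest on the same radiotherapy, so this table is where a reader checks that it was delivered alike. An imputed survival time would differ between arms whenever survival differs. At stake is the accuracy of a descriptive exposure table, not the primary result.

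**Working it through.** **Inputs from SAP Section 5.** Exponential OS; medians 13.0 and 18.0 months (HR 0.72); about 550 subjects randomized 1:1, so 275 per arm; 10 months of accrual plus 23 of follow-up, so a cut at 33 months. Uniform accrual is my assumption. A month is 30.4375 days, as in SAP 7.4.1, or 4.348 weeks.

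**Assumptions the documents do not supply.** A true course of mean 6.5 weeks and SD 0.5, and the fraction of end dates missing (1% to 10% shown).

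**Step 1: reproduce the plan's figures.** Schoenfeld's formula with two-sided alpha 0.05, 90% power and HR 0.72 gives 390 deaths, as stated. The critical HR is exp(-1.96 × 2/√390) = 0.82, as stated. The probability of death by month 33 is

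P = 1 - [exp(-23λ) - exp(-33λ)]/(10λ), with λ = ln 2/median.

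- RT + TMZ: λ = 0.0533, P = 0.773, or 212 deaths.
- RT + nivolumab: λ = 0.0385, P = 0.658, or 181 deaths.

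The total is 393, in line with 390 at 33 months.

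**Step 2: imputed duration when the end date is missing.** With the cap, this is the smaller of survival time and time to the cut, counted from the start of radiotherapy. Starting within a week of randomization hardly matters, because exponential survival has no memory. The mean is P/λ.

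| | RT + TMZ | RT + nivolumab |
|---|---|---|
| Mean, months | 14.49 | 17.08 |
| Mean, weeks | 63.0 | 74.3 |
| Median, weeks | 56.5 | 78.3 |
| Share over 52 weeks | 53% | 63% |
| Mean if surviving past 6.5 weeks | about 68 | about 78 |

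A subject alive at the cut with current follow-up would show 23 to 33 months, about 100 to 143 weeks.

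**Step 3: effect on the arm summary.** Reported mean = (1 - f) × 6.5 + f × M, where f is the fraction missing and M the imputed mean.

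| f | RT + TMZ | RT + nivolumab |
|---|---|---|
| 1% | 7.1 | 7.2 |
| 5% | 9.3 | 9.9 |
| 10% | 12.2 | 13.3 |

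At 1%, for example, 0.99 × 6.5 + 0.01 × 63.0 = 7.07. The spurious difference between arms at 1% is 0.01 × (74.3 - 63.0) = 0.11 weeks.

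The SD reacts more. The variance is (1 - f) × 0.5² + f × s² + f(1 - f)(M - 6.5)², where s is the SD of the imputed values. For RT + TMZ subjects surviving past 6.5 weeks, simulation gives s of about 41 weeks. At 1% this is 0.25 + 16.8 + 0.0099 × 61.5² = 54.5, an SD of 7.4 against 0.5. The same calculation gives 8.3 for RT + nivolumab. The median barely moves, and a single record is enough to set the maximum.

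**The case against.** The strongest reply is that the link to SAP 7.4.1 is not written down. That section speaks of dose start and dose end dates, the wording it also uses for temozolomide, while Appendix 2 speaks of procedures. No visible text says that study radiotherapy is entered on the RADIOTHERAPY page. If it is on another page, the appendix's own note sets the end date to missing and the problem disappears. Anchoring partial start dates to the first dose date fits non-study procedures at least as well, and SAP 7.4.3.3 has a separate use for subsequent radiotherapy. SAP 7.1 refers to Section 8 for date conventions, and its text is not visible. All of this stands, so the point has to be conditional.

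It is also fair that the size is modest. The missing fraction is assumed, Protocol 9.2.3 restricts blank CRF fields, the summary is not tested, and a 70-week course would stand out in the maximum and the listings. For a subject who died during radiotherapy the cap is roughly right, so the imputed date is implausible for most subjects rather than impossible for all.

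A reader might go further. Protocol 4.1 says that "Although not a medicinal product, Radiation Therapy is also considered part of study treatment", and SAP 6.1 counts adverse events "within a safety window of 30 days (or 100 days depending on the analysis) after the last dose of study treatment". One could infer that an imputed radiotherapy end date keeps the adverse event window and person-years open until death. The documents do not support that: no visible text lets a radiotherapy end date, imputed or not, set the last dose of study treatment.

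The reply does not remove the rule itself. It is current SAP text, it gives an implausible value for a fixed course, and it sits beside rules that leave comparable missing dates missing.

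**Conclusion.** The point holds in conditional form and is minor. The Appendix 2 rule is unsuitable for a missing, unknown or invalid radiotherapy end date. If the RADIOTHERAPY page feeds SAP 7.4.1, each affected record carries a survival time averaging about 63 weeks (RT + TMZ) or 74 weeks (RT + nivolumab), or about 68 and 78 among those surviving past 6.5 weeks.

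At an assumed 1% missing, the mean rises by 0.6 to 0.7 weeks from an assumed 6.5, and the SD and maximum are no longer usable as descriptions of radiotherapy. These sizes rest on the plan's exponential survival, uniform accrual and a 33-month cut.

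OS, cumulative Gy and the count of subjects below 90% of planned dose do not use the date. It should not be read as a finding that 7.4.1 certainly uses the imputed date, or that safety windows or person-years are affected; neither is shown.

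**What to change.** In SAP Appendix 2:

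- Apply the extraction-date rule only to records marked *continuing*.
- For study radiotherapy with a missing, unknown or invalid end date, use the last recorded radiotherapy dose date if the CRF collects one. The documents do not show that it does.
- Otherwise leave the end date and the duration missing, and report the number missing by arm.

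In SAP 7.4.1, name the CRF page that supplies the radiotherapy start and end dates. If study radiotherapy is on a different page, that sentence alone settles the matter, and the other changes do no harm.

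The cost is a few sentences, a small programming change and a few durations shown as missing. No clinical rule changes.

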4.5.1.6 Continuing Nivolumab with Suspected Progression

Accumulating evidence indicates that a minority of subjects treated with immunotherapy may derive clinical benefit despite initial evidence of disease progression, eg, due to inflammatory reaction simulating progression (“tumor flare” or pseudoprogression). Subjects on the RT + nivolumab arm may, at investigator discretion, continue nivolumab in the setting of suspected progression until progression is confirmed. [Note: this is not the same as confirmation of progression occurring within 12 weeks after RT, which applies to both treatment arms.] Communication with the BMS Medical Monitor is strongly encouraged. If the investigator believes that the subject continues to derive clinical benefit by continuing treatment, the subject should continue assessments according to [Table 5.1-2](#).

Subjects may continue nivolumab beyond initial (suspected) progression only if they meet the following criteria:

- Subject is tolerating nivolumab

- Treatment will not delay intervention to prevent imminent complications, eg surgery for relief of symptomatic intracranial mass effect
- Investigator-assessed overall clinical benefit

Radiographic assessment should be repeated after suspected progression as clinically required in order to determine whether there has been a decrease in the tumor size or continued progression. If possible, perfusion images should also be obtained. All MRI scans should be submitted to the imaging vendor as soon as possible.

Re-operation should be considered, if lesion is surgically accessible, to differentiate immune-treatment effects from progression. The BMS Medical Monitor should be consulted. Potential for clinical benefit should be balanced by clinical judgment as to whether the subject is clinically deteriorating and unlikely to receive benefit from continued treatment with nivolumab. Nivolumab treatment should be discontinued permanently upon confirmation of RANO-assessed progression but prolonged observation (eg, 3 months) may be required, as suggested in Okada et al.⁴⁰

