5.4.1 Suspected Progression

In order to distinguish potential treatment effects (or “pseudoprogession”) from progressive disease and thus to minimize premature discontinuation of nivolumab or temozolomide, subjects who initially meet radiologic criteria for disease progression, but are tolerating study drug, may continue receiving study drug until confirmation of progression with an MRI performed approximately 8 weeks later. If possible, MRI perfusion images should also be obtained. If a determination cannot be made after an 8 week interval, then treatment may continue until either progression is confirmed or regression is observed, consistent with either pseudoprogession or

immune-treatment effect. Consultation with the BMS Medical Monitor is recommended but not required.

Confirmation of progression is mandatory if recurrence occurs within 12 weeks of completion of RT. Suspected disease progression within 12 weeks after the end of RT must be confirmed by subsequent MRI performed within 8 weeks after the initial radiological assessment of progression. Prior to 12 weeks after RT, progression can only be defined using diagnostic imaging if there is new enhancement outside of the radiation field (beyond the high-dose region or 80% isodose line) or if there is unequivocal evidence of viable tumor on histopathologic sampling.³⁹ Note: in the absence of radiographic or histologic confirmation of progression, clinical decline alone is not sufficient for definition of progressive disease.

If the follow-up assessment confirms that progression has occurred, the date of progression will be the date at which progression was first determined. If the follow-up assessment does not confirm progression, then the original time point response will be assessed as SD.

[REDACTED]

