4.2 Secondary

[figure not shown]
4.2.1 *Progression Free Survival*

PFS is defined as the time from randomization to the date of the first documented tumor progression or death due to any cause. Subjects who did not have disease progression or who did not die will be censored at the date of last tumor assessment. Subjects who did not have any on study tumor assessment and did not have tumor progression or die will be censored at the randomization date. Subjects who started any subsequent anti-cancer therapy without a prior reported progression will be censored at the last tumor assessment prior to initiation of the subsequent anti-cancer therapy. Subjects who had surgical resection post start of study treatment will be censored at the last tumor assessment date prior to initiation of surgical resection. PFS will be determined by investigator reported response based on RANO criteria

The progression free survival rate at time T is defined as the probability that a subject has not progressed and is alive at time T following randomization.

Censoring rules for the primary analysis of PFS are presented in Figure 4.2.1-1 Alternate censoring rules for sensitivity analyses are specified in Section 7.5.3.2.

Figure 4.2.1-1: Graphic Display of PFS Primary Definition

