 - i) If month and year of surgery match month and year of first dose date then impute the missing date as the date of first dose;
 - ii) If month and year of surgery don't match month and year of first dose date then impute as first day of that month and year;
 - b) If both day and month are missing then impute as maximum between 01JAN of the year and date of the first dose;
 - c) If date is completely missing or invalid then leave missing.

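### Partial dates of surgery after treatment start go to the earliest allowed day with no visible check against progression, so a PFS event can become an earlier censored time

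*SAP*

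**What the plan says.** **Imputation (SAP Appendix 2, surgery rules).** For surgeries recorded on any CRF page other than the prior-surgery page, which the SAP treats as on-treatment or subsequent:

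- Day missing, same month as first dose: "then impute the missing date as the date of first dose".
- Day missing, any other month: "then impute as first day of that month and year".
- Day and month missing: "If both day and month are missing then impute as maximum between 01JAN of the year and date of the first dose".

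Procedure start dates, which include radiotherapy, follow the same earliest-day pattern. Appendix 2 does compare imputed procedure end dates with death or last known alive date. It shows no comparison of an imputed surgery date or procedure start date with progression.

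**Censoring (SAP 4.2.1; same rule in Protocol 8.3.2).** "Subjects who had surgical resection post start of study treatment will be censored at the last tumor assessment date prior to initiation of surgical resection". Subsequent anti-cancer therapy without an earlier reported progression is handled in the same way.

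**Order of progression and surgery.** Protocol 5.4.1 says that, once progression is confirmed, "the date of progression will be the date at which progression was first determined". Protocol Tables 5.1-2 and 5.1-3 foresee surgery at progression or suspected progression. Protocol 4.5.1.6, on continuing nivolumab, adds: "Re-operation should be considered, if lesion is surgically accessible, to differentiate immune-treatment effects from progression".

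**Testing.** SAP 7.5.3.1 tests PFS at the two-sided 5% level only after a positive OS result. It is the only secondary endpoint tested.

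**The concern.** The imputation rule and the censoring rule work against each other. Progression is dated when first determined, so a resection prompted by it comes later. If the resection date is incomplete, Appendix 2 pulls it to the start of the interval, often past the progression date. The subject then looks like someone resected while progression-free and is censored at a scan before the one that showed progression.

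For surgery prompted by progression the error runs one way only: an event can be lost, never gained. The resulting censoring is informative, because it removes subjects who are known to have progressed. It affects the primary PFS analysis, which is the one carried into the testing hierarchy.

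**Working it through.** The plan states no figure on this point, so there is none to reproduce. The check applies the stated rules to calendar dates.

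**Reading used.** The surgery clause in SAP 4.2.1 does not carry the limit to subjects without a prior reported progression that the subsequent-therapy clause has. I read it as applying only when resection precedes progression.

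**One subject (illustrative dates).** Clear MRI on 10 April, progression on MRI on 6 June, resection on 16 June recorded as June with no day. Appendix 2 gives 1 June. The last assessment before 1 June is 10 April. An event on 6 June becomes censoring on 10 April, 57 days earlier. If only the year were known and first dose fell in that year, the surgery would move to the first-dose date. No on-study scan would precede it, and censoring would fall back to about randomization.

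**Day missing: share reversed.** Let progression fall on day *p* of a month of *L* days, with surgery *g* days later. The imputed 1st precedes progression when both dates are in that month (*p* + *g* ≤ *L*) and *p* ≥ 2. That leaves *L* − *g* − 1 values of *p*. Over a 365-day year, for *g* up to 27:

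share = (365 − 12(*g* + 1)) / 365

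| Assumed gap | Calculation | Share reversed |
|---|---|---|
| 7 days | 269/365 | 74% |
| 14 days | 185/365 | 51% |
| 21 days | 101/365 | 28% |

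Day-by-day enumeration over 730 calendar days gives the same values (0.737, 0.507, 0.277), then 5% at 28 days and 0% at 35 days. The simpler same-month probability, (30.4 − *g*)/30.4, gives 77%, 54% and 31%. It is about 3 points high because a progression on the 1st is not preceded by an imputed 1st.

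**Day and month missing.** Imputing 1 January, and leaving aside the first-dose floor, the share is (365 − *g* − 1)/365: 357/365 = 98% at 7 days and 350/365 = 96% at 14 days.

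**Number of events.** Lost events = 550 × *r* × *m* × share. Here 550 is the planned sample size, *r* is the fraction resected after progression and *m* is the fraction of those dates lacking the day. Neither *r*, *m* nor the gap is in the documents, so all three are assumed.

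| *r* | *m* | Gap | Lost events |
|---|---|---|---|
| 10% | 1% | 21 days | 550 × 0.10 × 0.01 × 0.277 = 0.2 |
| 20% | 5% | 14 days | 550 × 0.20 × 0.05 × 0.507 = 2.8 |
| 30% | 10% | 7 days | 550 × 0.30 × 0.10 × 0.737 = 12.2 |

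**With an ordering check.** If the imputed date may not precede a documented progression inside the same partial interval, the share reversed is 0% at every gap, by construction.

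**The case against.** **The controlling text may lie elsewhere.** SAP 7.1 refers to Section 8 for the handling of partial dates, and SAP 4.2.1 refers to Figure 4.2.1-1 for the censoring rules. Neither could be read, and either could hold an ordering or tie rule. This stands as a limit: the problem is shown for the visible rules only.

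**Analyses that avoid it exist.** PFS sensitivity analyses 1 and 3 in SAP 7.5.3.2 count events after subsequent therapy or resection, so they do not depend on where the surgery date falls. They would help to expose a material effect. They do not change the tested analysis.

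**Many partial dates should be recoverable.** The protocol asks for tissue from surgery at progression to be submitted. Section 5.6.1.1 puts the collection date on the requisition form, and Section 9.2.3 requires CRF data to agree with source. This is a good reason to expect small numbers, but Appendix 2 governs whatever remains partial.

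**A bias between arms is not established.** A reader might infer from Protocol 4.5.1.6 that nivolumab subjects would lose more events. That section only asks that re-operation be considered where the lesion is accessible. Handling of suspected progression in 5.4.1 and tissue submission in Table 5.1-2 cover both arms, and no document gives resection rates by arm. SAP 7.4.3.3 also restricts subsequent surgery for tumors to resection, so a biopsy may not count.

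**Not every re-operation has an event to lose.** Surgery for suspected progression puts an event at risk only if a progression was documented with an earlier date.

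**Imputing late has its own bias.** Setting every partial date to the latest possible day would count progressions that truly followed surgery. That is a reason for a narrow rule, not for leaving the current one unchecked.

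**Conclusion.** On the visible text the concern holds: two stated rules combine to turn some progressions into earlier censored times in the primary PFS analysis. The shares of 74%, 51% and 28% depend on the assumed gaps and on progression dates spread evenly over the calendar. The total of about 0.2 to 12 lost events rests on assumed resection and partial-date rates, and the true number is probably low.

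A reader might take 1% to 3% of all 550 subjects, 6 to 17, as the number of events lost. That uses the wrong base: only subjects resected after progression, with a partial date and an order that imputation reverses, can lose an event. The documents also do not support a claim that the treatment comparison is biased toward either arm. A difference between arms is possible but not shown.

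OS is untouched and PFS is tested only after a positive OS result. This is a low-priority correction, worth making because it is cheap and concerns a tested endpoint.

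**What to change.** 1. Before database lock, query every partial date of on-treatment or subsequent surgery and radiotherapy, for example against the tissue-collection date on the requisition form.
2. For dates still partial, add to Appendix 2 that the imputed date may not precede a documented progression falling within the interval the partial date allows, and that a progression on the imputed date counts as the event. Otherwise keep the current rule. If Section 8 or Figure 4.2.1-1 already says this, cite it in Appendix 2.
3. State in SAP 4.2.1 whether censoring at resection applies only when no progression has been reported before it.
4. Report by arm the number of partial dates and the number of subjects whose PFS status depends on the rule, and repeat PFS under the current rule as a sensitivity analysis.

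The cost is a few lines of SAP text, a small programming change and some data queries. The downside is that an occasional progression that truly followed surgery within the same interval would be counted as an event. The sensitivity analysis in step 4 shows whether that matters.
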